## 8.2 Guidelines for Determining Causality

The investigator will use the following question when assessing causality of an adverse event to study drug where an affirmative answer designates the event as a suspected adverse reaction: Is there a reasonable possibility that the drug caused the event? “Reasonable possibility” means there is evidence to suggest a causal relationship between the drug and the adverse event.

## 8.3 Reporting Procedures

Relevant clinical and safety laboratory data will be entered into the data coordinating center (DCC) AdvantageEDCSM at the study site within 7 business days of data acquisition. The DCC data management personnel will monitor the occurrence of the events listed below and notify the DMC, safety monitors, investigators, NIH/NICHD, and PTN staff if any of the halting criteria are met. A decision to proceed or to terminate the trial will be made by the sponsor and the NIH/NICHD. The DMC may request review of the data if deemed necessary.

### 8.3.1 Adverse Event Reporting

All AEs will be entered into the safety data system within 7 days of identification. SAEs will be entered into the data system within 24 hours of identification. If there are any technical difficulties, the SAE will be reported to the DCC by telephone or fax communication. At the earliest, the SAE should also be entered into the EDC. Any SAE entered in the EDC will generate an automatic email notification to the DCC, IND sponsor, and funding sponsor. The BPCA medical monitor will review all SAEs at the time they are reported. Investigators must also submit safety reports locally as required by their IRB.

### 8.3.2 Regulatory Reporting

Any event that requires expedited reporting based on federal regulations will be forwarded to the IND sponsor. The IND sponsor or its representative will submit expedited safety reports (IND safety reports) to the FDA and other regulatory agencies as necessary, and will inform the investigators of such regulatory reports. Site investigators must submit IND safety reports as required by their IRB. Documentation of the submission and receipt by the IRB must be retained for each IND safety report. All serious events designated as “not related” to study product(s) will be reported to the FDA at least annually in a summary format.

## 8.4 Halting or Discontinuation

A participant’s parent/guardian may voluntarily discontinue participation in this study at any time. The participant’s parent/guardian is not obligated to state the reason for withdrawal. The reasons for withdrawal, or failure to provide a reason, must be documented by the investigator on the completion/withdrawal section of the CRF.

Participant safety data will be reviewed on an ongoing basis to monitor for halting criteria. The study enrollment and dosing will be halted for 1 or more of the drugs in this study for a safety review if serious suspected adverse reactions or serious adverse reactions occur in 2 or more participants within each drug group. Enrollment to any remaining drug(s) will continue.

This information will be submitted to the BPCA DMC, NICHD, and FDA along with an analysis and future plans for the study.

Furthermore, the NICHD, the IND sponsor, the DMC, and the investigator shall have the right to recommend termination of 1 or more of the drugs in this study at their discretion. Enrollment to any remaining drug(s) will continue. Possible reasons for termination of the study include, but are not limited to:

1. Adverse events
2. Unsatisfactory enrollment with respect to quantity or quality
3. Inaccurate or incomplete data collection
4. Falsification of records
5. Failure to adhere to the protocol

Note: Participants withdrawn from the study due to an AE, whether serious or non-serious, must be followed by the investigator until the clinical outcome from the AE is determined. The AE(s) should be noted on the appropriate eCRFs, and the participant's progress should be followed until the AE is resolved or considered stable. The medical monitor or study PI must be notified if the AE may relate to overdose of study treatment; the package insert should be consulted for details of any specific actions to be taken.

## 8.5 Safety Oversight

A qualified and experienced physician not otherwise associated with this protocol will serve as the medical monitor. The medical monitor will review all SAEs at the time they are reported. If safety concerns are identified, the medical monitor may request a meeting of the DMC to review safety data. At a minimum, the medical monitor will comment on the outcomes of the SAE and causal relationship of the SAE to the study product. The medical monitor will also indicate whether he/she concurs with the details of the report provided by the study investigator. If no SAEs prompt review at an earlier time point, the DMC will review AEs and SAEs quarterly. The DMC will convene and make recommendations on termination of the study based on review of safety reports and halting rules. The safety data will be compiled by the DCC. Based on the recommendations of the DMC, PTN, and NIH/NICHD, the IND sponsor will make a decision to terminate or continue the study.

## **9 CLINICAL MONITORING**

Site monitoring will be conducted to ensure that human participant protection, study procedures, laboratory procedures, study intervention administration, and data collection processes are of high quality and meet sponsor, GCP/ICH, and regulatory guidelines, and that the study is conducted in accordance with the protocol and DCC or DCRI sponsor standard operating procedures. The IND sponsor, or as detailed in the Transfer of Regulatory Obligations (TORO), the DCC, NIH/NICHD, or its designee will conduct site-monitoring visits as detailed in the monitoring plan or in the manual of procedures.

Site visits will be made at standard intervals as defined by the site monitoring plans and may be made more frequently as directed by the IND sponsor and NIH/NICHD. Monitoring visits will include, but are not limited to, review of regulatory files, accountability records, data collection forms (DCFs), informed consent forms, medical and laboratory reports, and protocol compliance. Study monitors will meet with investigators to discuss any problems and actions to be taken and document visit findings and discussions.

## 10 STATISTICAL CONSIDERATIONS

### 10.1 Study Outcome Measures

PK of these 3 antimicrobials.

### 10.2 Sample Size Considerations

The sample size is based on the ability to observe a serious toxicity rate and to describe the PK. A sample size of 32 participants will provide adequate precision in the PK parameter estimates (i.e., CL) that will be dependent on the underlying variability of the parameter (see table below). For example, assuming an inter-individual coefficient of variance (CV%) of 40% in the population CL parameter estimate after weight-based allometric and maturation scaling, a sample size of 32 participants would provide a margin of error of  $\pm 14\%$  in the 95% confidence interval (CI) of the CL estimate.

The sample size is sufficient to describe the PK of these 3 antimicrobials.

PK Parameter CV%	95% CI Margin of Error
40%	$\pm 14\%$
50%	$\pm 17\%$
60%	$\pm 21\%$
80%	$\pm 28\%$

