## **PROTOCOL SYNOPSIS**

Protocol Title:	Pharmacokinetics of Antistaphylococcal Antibiotics in Infants
Phase:	I
Product:	Rifampin, ticarcillin-clavulanate, clindamycin
Objectives:	Primary: Describe the pharmacokinetics (PK) of rifampin, ticarcillin-clavulanate, and clindamycin in infants  Secondary: Describe the safety profile of rifampin, ticarcillin-clavulanate, and clindamycin in infants
Study Design:	Multiple center, open-label, PK study
Study Population:	Hospitalized infants: 1. Rifampin: <121 days postnatal age (PNA) 2. Ticarcillin-clavulanate: <91 days PNA AND <30 weeks gestational age (GA) 3. Clindamycin: <121 days PNA AND <30 weeks GA
Number of Participants:	16–32 evaluable per study drug
Number of Sites:	Approximately 15 sites
Duration of Participant Participation:	Approximately 30 days
Dose Duration:	Study drug will be administered for 2–4 days
Estimated Start:	July 2012
Estimated Time to Complete Enrollment:	Approximately 24 months

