## 5 Study Population

### 5.1 Selection of the Study Population

**Rifampin:** 16 to 32 evaluable participants, at least 4 in each group

- Group 1: GA <32 weeks, PNA <14 days
- Group 2: GA <32 weeks, PNA ≥14 days–120 days
- Group 3: GA ≥32 weeks, PNA <14 days
- Group 4: GA ≥32 weeks, PNA ≥14 days–120 days

**Ticarcillin-clavulanate:** 16 to 32 evaluable participants, at least 4 in each group

- Group 1: GA <30 weeks, PNA <14 days
- Group 2: GA <30 weeks, PNA ≥14 days–45 days
- Group 3: GA <30 weeks, PNA >45 days–90 days

**Clindamycin:** 16 to 32 evaluable participants, at least 4 in each group

- Group 1: GA <30 weeks, PNA <14 days
- Group 2: GA <30 weeks, PNA ≥14 days–45 days
- Group 3: GA <30 weeks, PNA >45 days–120 days

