#### Population for Analysis

All participants who receive at least 1 dose of study drug will be evaluable for safety profile analysis. All participants that provide at least 1 PK sample will be included in the PK analysis.

Pharmacokinetic data from premature infants collected in the Pharmacokinetics of Understudied Drugs Administered to Children per Standard of Care (POPS) trial will be combined and co-modeled with data from the Staph Trio trial. Inclusion of POPS data will increase the sample size across all cohorts, allow for model evaluation/validation using data from an independent trial and likely result in more precise estimation of model parameters.

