#### **Interim PK analysis**

**Rifampin:** An interim PK analysis will be performed after enrollment of 3 participants in each cohort for rifampin. If the interim analysis suggests the PK data are sufficient to describe rifampin disposition in this patient population, enrollment will stop after 8 participants are enrolled in each cohort. If additional participants are required, the interim PK data will be used to determine the number of additional participants.

**Clindamycin:** An interim PK analysis will be performed after enrollment of 3 participants in cohort 1 for participants  $\leq 26$  weeks gestational age. If the interim analysis suggests the PK data are sufficient to describe clindamycin disposition in this patient population, enrollment will stop after 8 participants are enrolled in each cohort. If additional participants are required, the interim PK data will be used to determine the number of additional participants.

For both analyses, if the PK analysis suggests that drug exposure is below the maximum tolerated exposure in adults, no dosing modifications will be made.

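### Section 10.2 gives clearance precision only at 32 participants, yet clindamycin may stop at 24 enrolled and ticarcillin-clavulanate may end anywhere from 16 to 32 evaluable

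*Protocol*

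**What the plan says.** Section 10.2 of the protocol states: "A sample size of 32 participants will provide adequate precision in the PK parameter estimates (i.e., CL"). Its table gives the 95% margin of error for a PK parameter as ±14%, ±17%, ±21% and ±28% for CVs of 40%, 50%, 60% and 80%. The only sample size named is 32. The section also concludes: "The sample size is sufficient to describe the PK of these 3 antimicrobials".

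Other sections set the size of each drug group differently:

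- The synopsis plans "16–32 evaluable per study drug". Section 5.1 repeats this for every drug: "16 to 32 evaluable participants, at least 4 in each group".
- Section 5.1 lists four groups for rifampin and three each for ticarcillin-clavulanate and clindamycin. The last clindamycin group is "Group 3: GA <30 weeks, PNA >45 days–120 days".
- Section 10.3 (Interim PK analysis) makes clindamycin's stop conditional: "If the interim analysis suggests the PK data are sufficient to describe clindamycin disposition in this patient population", enrollment ends at 8 per cohort; otherwise the interim data decide how many infants to add. Rifampin has the same two branches. Ticarcillin-clavulanate has no interim rule.
- Section 10.2 (Population for Analysis) says "All participants that provide at least 1 PK sample will be included in the PK analysis", and that data from the separate POPS trial will be co-modeled: "Inclusion of POPS data will increase the sample size across all cohorts". It gives no number of POPS infants, and the precision table does not use them.

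**The concern.** The table describes the top of the planned range, but the sentence that draws on it covers all three drugs. A reader would take ±14% to ±28% as the clearance precision planned for each drug. The design leads to 32 for rifampin only. For clindamycin it allows a stop at a smaller number, and for ticarcillin-clavulanate it fixes no number within the range.

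Clearance is one of the primary outcomes in section 3.1.1, and this table is the protocol's only numerical statement of precision. If it does not apply to two of the three drugs, the sufficiency statement has no figure behind it for them. The interim rule supplies none either, since section 10.3 gives no numerical criterion for judging the PK data sufficient.

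A smaller, related point is that the unit of counting shifts. Section 5.1 counts evaluable infants, the interim rule counts enrolled infants, section 10.2 refers simply to participants, and the PK analysis set takes anyone with one PK sample. The number to be entered in the precision formula is therefore not settled.

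**Working it through.** **Inputs**

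- CV of clearance: 40%, 50%, 60%, 80% (section 10.2 table).
- Two-sided 95% confidence (section 10.2).
- N = 32 (section 10.2); N = 16 as the lower end of the range (synopsis and section 5.1); N = 24 for clindamycin, derived below.

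**Step 1: sizes the design leads to**

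- Rifampin: 4 cohorts × 8 = 32 enrolled at the stop; the other branch adds infants.
- Clindamycin: 3 cohorts × 8 = 24 enrolled at the stop; the other branch adds infants.
- Ticarcillin-clavulanate: 16 to 32 evaluable, with no rule selecting a value. The group minimum gives only 3 × 4 = 12, so the floor of 16 is what binds.

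**Step 2: reproduce the protocol's table**

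Margin = 1.96 × CV / √N. At N = 32, √32 = 5.657:

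- CV 40%: 1.96 × 40 / 5.657 = 13.86%
- CV 50%: 1.96 × 50 / 5.657 = 17.32%
- CV 60%: 1.96 × 60 / 5.657 = 20.79%
- CV 80%: 1.96 × 80 / 5.657 = 27.72%

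These round to 14, 17, 21 and 28, which are all four rows. With the t quantile on 31 degrees of freedom (2.040) the results are 14.4, 18.0, 21.6 and 28.8. They round to 14, 18, 22 and 29 and miss three rows. The table therefore uses the normal quantile and is arithmetically right.

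**Step 3: same formula at the other sizes, trial data alone**

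| CV | N = 32 | N = 24 | N = 16 |
|---|---|---|---|
| 40% | ±13.9% | ±16.0% | ±19.6% |
| 50% | ±17.3% | ±20.0% | ±24.5% |
| 60% | ±20.8% | ±24.0% | ±29.4% |
| 80% | ±27.7% | ±32.0% | ±39.2% |

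Relative width against N = 32: √(32/24) = 1.155, so 15% wider at 24; √(32/16) = 1.414, so 41% wider at 16. Of the eight margins at 24 and 16, three lie outside the range the protocol displays (CV 80% at 24; CV 60% and 80% at 16), and the other five lie inside it.

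**Step 4: sensitivity to the quantile**

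With t quantiles (2.069 on 23 degrees of freedom, 2.131 on 15) the margins for the four CVs are ±16.9, 21.1, 25.3 and 33.8% at N = 24, and ±21.3, 26.6, 32.0 and 42.6% at N = 16. The figures in Step 3 are the more favourable version.

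**The case against.** The strongest reply is that nothing here is contradictory. Section 10.2 says correctly what 32 infants deliver, and 32 lies within an openly stated range. The study is a descriptive phase I study with no hypothesis test and no precision target, so 24 or 16 cannot miss one, and ±28% is only the last row of a table, not an acceptance limit. Clindamycin stops at 24 only if the interim PK data are judged sufficient, and at the protocol's worked CV of 40% the loss there is about two percentage points (13.9% to 16.0%). The planned analysis also pools POPS data, so margins on trial data alone understate the final precision.

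Much of this stands, and it limits the point. The table is not wrong, smaller sizes are not shown to be inadequate, the change at 24 is modest, and the 41% widening belongs to the floor of the range, which chiefly concerns ticarcillin-clavulanate. It does not remove the mismatch. The sufficiency statement covers three drugs, while its only numerical support fits one. POPS cannot fill the gap as written, because the protocol neither gives a number nor uses those data in section 10.2.

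On the counting unit, the replacement paragraph in section 10.2 partly links enrolled to evaluable infants by letting those with fewer than 3 evaluable PK samples be replaced. Replacement is optional, however, so 24 enrolled may still yield fewer than 24 evaluable. That part is secondary and would not merit a comment alone.

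**Conclusion.** The concern holds. The margins in section 10.2 are correct for 32 participants and fit rifampin, apart from any shortfall of evaluable against enrolled infants. They do not describe clindamycin if it stops at 24 enrolled, where margins run from ±16.0% to ±32.0%. Nor do they describe ticarcillin-clavulanate at any size below 32; at the floor of 16 they run from ±19.6% to ±39.2%.

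These figures assume the protocol's own normal-approximation formula, its CV values, trial data alone, and every counted infant contributing to the estimate. Pooled POPS data could narrow the margins by an amount that cannot be calculated from the protocol. The conclusion concerns the support given for the sample size; it is not a finding that the trial is too small.

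**What to change.** In section 10.2:

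1. Add columns to the table for N = 16 and N = 24 beside N = 32, labelled as trial data alone.
2. Replace the single sufficiency sentence with one for each drug, tied to the size that drug will reach: 32 enrolled for rifampin and 24 enrolled for clindamycin at their interim stops, and for ticarcillin-clavulanate either a fixed target or the whole 16 to 32 range.
3. If sufficiency relies on POPS data, state the number of POPS infants assumed for each drug.
4. Use one counting unit, evaluable or enrolled, in section 5.1, section 10.2 and the interim rule of section 10.3, and say how it relates to the PK analysis set.

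The cost is wording and two table columns, with no added participants or time. The stated precision becomes less favourable for clindamycin and ticarcillin-clavulanate.

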#### Replacement Participants

If participants have <3 evaluable PK samples (not scavenged or dried blood spots), additional participants may be enrolled to ensure appropriate analysis. Evaluable samples are defined as samples with adequate volume and integrity to generate accurate concentration results as well as their associated dosing and sample times data.

#### Population for Analysis

All participants who receive at least 1 dose of study drug will be evaluable for safety profile analysis. All participants that provide at least 1 PK sample will be included in the PK analysis.

Pharmacokinetic data from premature infants collected in the Pharmacokinetics of Understudied Drugs Administered to Children per Standard of Care (POPS) trial will be combined and co-modeled with data from the Staph Trio trial. Inclusion of POPS data will increase the sample size across all cohorts, allow for model evaluation/validation using data from an independent trial and likely result in more precise estimation of model parameters.

### 10.3 Analysis Plan

Descriptive statistics such as number of observations, mean, median, 95% confidence interval, standard deviation, standard error, minimum, and maximum will be presented by gestational

age and postnatal age group for continuous variables (such as age, weight, etc.). Other descriptive statistics such as counts, proportions, and/or percentages will be presented by gestational age and postnatal age group to summarize discrete variables (such as race, sex, etc.).

### **Demographic and Baseline Characteristics**

The number of participants completed and discontinued early from study and the reasons for discontinuation will be summarized. Demographic and baseline characteristics will also be summarized. Variables include race, age, sex, and selected clinical variables recorded prior to initiation of study drug. Study drug administration will be summarized in terms of number of days of dosing and reasons for final discontinuation of study drug.

### **Safety and Clinical Laboratory Analyses**

The number of AEs, suspected adverse reactions, and adverse reactions will be summarized overall, by severity, and by each Medical Dictionary for Regulatory Activities (MedDRA) system organ class and preferred term. Prior and concomitant medications will be summarized by World Health Organization (WHO) drug class. Laboratory data, such as hematology and serum chemistry data, will be tabulated by GA and PNA group. Summary statistics for changes from baseline will be presented. Continuous laboratory measurements will be described at each visit using univariable descriptive statistics (mean, median, etc.); observed values and changes from baseline will be summarized. Lab tests reflective of liver toxicity (e.g., ALT, AST) will be further summarized in terms of the most extreme values and largest changes from baseline (in the appropriate direction) observed from start of study drug through the end of therapy.

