### 2.2.1 Potential Risks

It is the investigator's responsibility to ensure that, prior to initiating this study, this protocol is reviewed and approved by the appropriate local IRB. The composition and conduct of this committee must conform to the U.S. CFR, including provisions outlined in 45 CFR 46 subpart D.

Clindamycin and rifampin are protein-bound drugs. There are theoretical risks of increased bilirubin in infants with elevated bilirubin.

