### Risks of Rifampin

From the FDA label and review of the literature, side effects in patients administered rifampin include impacts to: gastrointestinal system (heartburn, anorexia, nausea, vomiting, jaundice, flatulence, cramps, and diarrhea); blood (low platelets occurred primarily with high-dose intermittent therapy; this effect is reversible if the drug is discontinued as soon as bruising occurs); central nervous system (headache, fever, drowsiness, fatigue, trouble walking, dizziness, inability to concentrate, mental confusion, behavioral changes, pains in arms or feet, and generalized numbness); renal system (elevations in kidney laboratory values [blood urea nitrogen {BUN} and serum uric acid] have been reported and are reversible when rifampin is discontinued and appropriate therapy instituted); and skin (skin reactions are mild and self-limiting and do not appear to be allergic reactions).

Rifampin has the potential to act as a strong inducer of the metabolism of drugs that are CYP450 substrates, and such concomitantly administered drugs should be monitored for potential lack of efficacy during concurrent treatment with rifampin and for 1 month after discontinuation of rifampin therapy.

Rifampin should not be used as monotherapy. Empirical anti-staphylococcal therapy of an appropriate anti-staphylococcal antibiotic should be used in combination with rifampin.

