### **Risks of Ticarcillin-clavulanate**

From the FDA label and review of the literature, side effects of ticarcillin-clavulanate, as with other penicillins, include the following adverse reactions: hypersensitivity (skin rash, pruritus, urticaria, arthralgia, myalgia, drug fever, chills, chest discomfort, erythema multiforme, toxic epidermal necrolysis, Stevens-Johnson syndrome, and anaphylactic reactions); central nervous system (headache, giddiness, neuromuscular hyperirritability, or convulsive seizures); gastrointestinal disturbances (disturbances of taste and smell, stomatitis, flatulence, nausea, vomiting and diarrhea, epigastric pain, and pseudomembranous colitis have been reported; onset of pseudomembranous colitis symptoms may occur during or after antibiotic treatment); hemic and lymphatic systems (thrombocytopenia, leukopenia, neutropenia, eosinophilia, reduction of hemoglobin or hematocrit, and prolongation of prothrombin time and bleeding time); abnormalities of hepatic function tests (elevation of serum aspartate aminotransferase [SGOT], serum alanine aminotransferase [SGPT], serum alkaline phosphatase, serum lactate dehydrogenase [LDH], serum bilirubin; there have been reports of transient hepatitis and cholestatic jaundice, as with some other penicillins and some cephalosporins); renal and urinary effects (hemorrhagic cystitis, elevation of serum creatinine and/or BUN, hypernatremia, reduction in serum potassium and uric acid); and local reactions (pain, burning, swelling, and induration at the infusion site and thrombophlebitis with intravenous administration).

Available safety data for pediatric patients treated with ticarcillin-clavulanate demonstrate a similar adverse event profile to that observed in adult patients.

Ticarcillin-clavulanate should not be used as monotherapy when methicillin-resistant *Staphylococcus aureus* is suspected.

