### **Risks of Clindamycin**

From the FDA label and review of the literature, the following are adverse reactions of clindamycin: antibiotic-associated colitis, pseudomembranous colitis, abdominal pain, nausea, and vomiting; hypersensitivity reactions (maculopapular rash and urticaria have been observed during drug therapy; generalized mild-to-moderate morbilliform-like skin rashes are the most frequently reported of all adverse reactions; rare instances of erythema multiforme, some resembling Stevens-Johnson syndrome, have been associated with clindamycin; a few cases of anaphylactoid reactions have been reported); skin and mucous membranes (pruritus, vaginitis, and rare instances of exfoliative dermatitis have been reported); liver (jaundice and abnormalities in liver function tests have been observed during clindamycin therapy); renal system (although no direct relationship of clindamycin to renal damage has been established, renal dysfunction as evidenced by azotemia, oliguria, and/or proteinuria has been observed in rare instances); hematopoietic (transient neutropenia [leukopenia] and eosinophilia have been reported; reports of agranulocytosis and thrombocytopenia have been made; no direct etiologic relationship to concurrent clindamycin therapy could be made in any of these instances); local reactions (pain, induration, and sterile abscess have been reported after intramuscular injection

---

and thrombophlebitis after intravenous infusion); musculoskeletal (rare instances of polyarthritis have been reported); and cardiovascular (rare instances of cardiopulmonary arrest and hypotension have been reported following too-rapid intravenous administration).

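### Per-infant worst on-drug values are planned only for liver tests, not for the platelet and neutrophil counts that the protocol's own risk lists name

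*Protocol*

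**What the plan says.** The laboratory paragraph of section 10.3 (Safety and Clinical Laboratory Analyses) has two levels.

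- **All laboratory tests.** "Laboratory data, such as hematology and serum chemistry data, will be tabulated by GA and PNA group". Further, "Continuous laboratory measurements will be described at each visit using univariable descriptive statistics (mean, median, etc.); observed values and changes from baseline will be summarized".
- **Liver tests only.** A second level is added for this class: "Lab tests reflective of liver toxicity (e.g., ALT, AST) will be further summarized in terms of the most extreme values". It also takes in each infant's biggest shift away from the baseline value, in whichever direction signals harm, between the first dose and the close of treatment.

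The risk sections under 2.2.1 list blood-count effects for each drug:

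- Rifampin: "low platelets occurred primarily with high-dose intermittent therapy".
- Ticarcillin-clavulanate: "thrombocytopenia, leukopenia, neutropenia, eosinophilia, reduction of hemoglobin or hematocrit".
- Clindamycin: "reports of agranulocytosis and thrombocytopenia have been made". The same list also gives transient neutropenia.

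Section 6.6.1 has sites record any hematocrit, white cell count, platelet count and differential obtained from 72 hours before the first dose to 72 hours after the last. Table 4 treats the whole therapy period, Day 1 to Day 2 or 4, as Visit 1.

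**The concern.** The protocol itself treats by-visit description as insufficient where it has a toxicity in mind, because it adds a per-infant worst-value summary for liver tests. It does not extend this to blood counts, although its own risk lists name them for every study drug, and it gives no reason for the difference.

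A drop in platelets or neutrophils is usually a brief low point in one or two infants. In cohorts that may hold as few as 4 infants, a safety table is useful largely because it shows that low point. At stake is the completeness of the secondary outcome, the safety profile. The primary pharmacokinetic outcomes are not affected.

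**Working it through.** The plan states no figure on this point, so there is none to reproduce. The check compares sections of the protocol and adds a small illustration with assumed values.

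**Step 1. Named risk, recorded test, worst-value summary.**

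| Test | Drugs whose risk list names a fall | Recorded (6.6.1) | Extreme-value summary (10.3) |
|---|---|---|---|
| Platelets | Rifampin, ticarcillin-clavulanate, clindamycin | Yes | Not named |
| Neutrophils | Ticarcillin-clavulanate, clindamycin | Yes, through white cell count and differential | Not named |

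**Step 2. Does the planned by-visit summary hide a single nadir?** Assume platelets of 250 × 10⁹/L in every infant, and one infant who falls to 40. Mean = (250 × (n − 1) + 40) / n.

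| n | Mean | Median | Minimum |
|---|---|---|---|
| 4 | (750 + 40)/4 = 197.5 | 250 | 40 |
| 8 | (1750 + 40)/8 = 223.75 | 250 | 40 |
| 32 | (7750 + 40)/32 = 243.4 | 250 | 40 |

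The mean and median dilute the fall, but the minimum shows it at every size. The opening of section 10.3 lists minimum and maximum among its statistics for continuous variables. So one low value is visible, provided it is the value that enters the visit summary.

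**Step 3. Does the low value always enter?** Table 4 places all dosing days in Visit 1. Section 6.6.1 records any value obtained on drug, so an infant may have several. Its rule for multiple values covers only the 72 hours before the first dose (the value closest to enrollment). No on-therapy rule is given. Assume a baseline of 250 and on-drug values of 250, 40 and 150 within Visit 1.

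| Value used for the visit | Value shown | Change from baseline |
|---|---|---|
| Last | 150 | 150 − 250 = −100 |
| Average | (250 + 40 + 150)/3 = 146.7 | 146.7 − 250 = −103.3 |
| Lowest | 40 | 40 − 250 = −210 |

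Under the first two conventions the nadir has gone before any cohort statistic is computed, and the cohort minimum cannot recover it. The liver-test rule avoids this by taking the extreme over the whole on-drug period.

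**Step 4. The adverse event route.** Section 8.1.1 makes a laboratory change an adverse event when the investigator considers it clinically significant, and section 10.3 tabulates adverse events by severity, system organ class and preferred term. A fall that is not so judged appears only in the laboratory tables. Section 8.1.3 notes that all participants will have pre-existing conditions, so this judgment is made against an abnormal background.

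**The case against.** The strongest reply is that little is lost. Minimum and maximum are listed in 10.3, the by-visit list is open-ended, changes from baseline are included, and a marked fall would very probably be reported as an adverse event and seen in the quarterly data monitoring committee review. Which tests get a worst-value row, and which draw represents a visit, are normally settled in the statistical analysis plan. The risk lists also come from labels and literature, with qualifiers: rifampin's low platelets are tied mainly to high-dose intermittent use, while the protocol's own rifampin schedule is daily; for the clindamycin blood-count reports the protocol says no direct causal link could be made.

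Most of this stands, and it limits the point. Two stronger readings that a reader might infer are not supported:

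- *Blood counts will appear only as averages that hide a single infant's nadir.* Step 2 shows otherwise: a listed minimum displays a single low value when that value is the one used.
- *Bilirubin is left out, although section 2.2.1 says* "There are theoretical risks of increased bilirubin in infants with elevated bilirubin". ALT and AST are given only as examples of liver tests, and total bilirubin plausibly belongs to that class.

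Nor do the risk lists show that the protocol expects these effects; they show only that it names them.

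The reply does not remove the gap for several values within one visit, or for a fall not judged clinically significant. The same by-visit tables and adverse event route apply to liver tests, and the protocol still adds a worst-value summary there. That choice of tests is made in the protocol, not left open.

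**Conclusion.** The point holds in a limited form. Section 10.3 names per-infant extremes and largest changes for liver tests only, while platelets (three drugs) and neutrophils (two drugs) are named risks, are already recorded, and lack the same safeguard. A nadir can be lost when an infant has several on-drug values in Visit 1, or when a fall is not called an adverse event. In the illustration, a fall of 210 would be shown as about 100.

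The size depends on assumptions: the platelet values are invented, the number of on-drug draws per infant is unknown, and the visit-value rule may be set in a statistical analysis plan that was not available. This is a low-cost improvement to a descriptive secondary analysis. It does not show that the safety analysis is invalid.

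**What to change.** In section 10.3, extend the existing summary of most extreme value and largest change from baseline, start of study drug through end of therapy, to at least platelets and neutrophils or white cells, in the downward direction. Present it by drug and cohort, with the number of infants who have a post-baseline value, since section 6.6.1 records whatever counts were obtained and that number may vary. Hematocrit, BUN, sodium and potassium could be added in the same way but are optional. If the sponsor prefers to keep the summary for liver tests alone, one sentence giving the reason would do.

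Cost: a few table rows and a sentence of text. No new samples, data fields or visits are needed.
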